Original Article NCT03615755

Short Duration Hyperbaric Oxygen Therapy to Improve HbA1c, Leukocyte, and Serum Creatinine in Patient with Diabetic Foot Ulcer Wagner 3-4

Author:

dr. [name]

Surgery Department, Faculty of Medicine, Udayana University, Sanglah General Hospital, Denpasar, Indonesia.

Co-Author 1:

Dr. dr. [name], Sp.B, Sp.BTKV

Thorax and Cardiovascular Surgery Division, Surgery Department, Faculty of Medicine, Udayana University, Sanglah General Hospital, Denpasar, Indonesia.

Co-Author 2:

[name]. dr. [name], Sp.PD-KGH

Nephrology and Hypertension Division, Internal Medicine Department, Faculty of Medicine, Udayana University, Sanglah General Hospital, Denpasar, Indonesia.

Correspondence:

Name : dr. [name]
[contact]
Email : [contact]
Affiliation : Surgery Department, Faculty of Medicine, Udayana University, Sanglah General Hospital, Denpasar, Indonesia.
Address : [name].

Denpasar, 10-04-2018

dr. [name]

Methods

This study uses pretest and posttest control group design, to know the role of standard therapy and combination therapy (standard therapy with adjuvant HBOT) to decrease HbA1c levels, leukocyte count, and serum creatinine levels in DFU patient Wagner 3-4. All DM patients with DFU at Sanglah General Hospital, Denpasar who meet the inclusion and exclusion criteria and willing to follow the research procedure. All patients are signing the agreement paper after getting research explanation. All patients were briefed on the study research using HBOT. If they are willing to participate in the study and use HBOT was grouped to combination therapy, if they are willing to participate in the study but do not want to use HBOT was grouped to standard therapy, but if they are not willing participate then excluded. The study was approved by Institutional Review Board of Medical Faculty of Udayana University and Sanglah General Hospital Denpasar with the ethical number 580/UN.14.2/KEP/2016.

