Thirty diabetic patients with DFU Wagner 3-4 were participated in this study. All patients were taken blood test for HbA1c levels, leukocyte count, and serum creatinine levels before debridement, then grouped for standard therapy or standard therapy with 10 sessions of HBOT. One session of HBOT uses oxygen at 2.4 ATA for 90 minutes per day at multiplace hyperbaric chamber. This therapy is given five sessions in a week, so it takes two weeks. At the end of therapy, all blood tests were performed again in both groups.

The inclusion criteria were patients who had type 2 diabetes and DFU Wagner class 3 or 4, aged over 18 years, and underwent debridement with or without toe amputation. The exclusion criteria were patients who had severe organs dysfunction such as heart failure, pulmonary infection, pneumothorax, chronic obstructive pulmonary disease, and stroke.

Statistical analysis using SPSS 17.0 (SPSS Inc., Chicago, IL, USA). All variables were described before and after treatment. Analysis pretest and posttest values on both groups were used paired T-test and independent T-test. The statistical test results are significant if $p < 0.05$.

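### HbA1c is re-measured once, at the end of a two-week course, so it gives only an early, partial reading of glycaemia and a null result would be inconclusive

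*Protocol*

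**What the plan says.** The title and the aim in the protocol's Methods both name HbA1c. The aim is to learn whether standard therapy, alone or combined with hyperbaric oxygen, serves "to decrease HbA1c levels, leukocyte count, and serum creatinine levels in DFU patient Wagner 3-4".

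The procedure paragraph of Methods fixes two measurement times. The first: "All patients were taken blood test for HbA1c levels, leukocyte count, and serum creatinine levels before debridement". The second follows the course of treatment: "This therapy is given five sessions in a week, so it takes two weeks. At the end of therapy, all blood tests were performed again". This re-test applies to either group. No later HbA1c is described, and the panel is HbA1c, leukocyte count and serum creatinine only.

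On sample size: "Thirty diabetic patients with DFU Wagner 3-4 were participated in this study"; the split by group is not given. On analysis: "Analysis pretest and posttest values on both groups were used paired T-test and independent T-test", with significance at p < 0.05. The text does not say whether the independent t-test compares post-test values or changes.

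**The concern.** HbA1c reflects glycaemia averaged over the life of the circulating red cells. Two weeks is short against that window, so most of the HbA1c at the re-test was formed before treatment began. Any change in glycaemia during the course appears in diluted form, while the trial is small.

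Two misreadings are at stake. A null two-week difference could be taken as no glycaemic effect when a worthwhile one is still compatible with the data. A significant difference could be taken as the full HbA1c effect when it is only part of it. The outcome and its measurement time are fixed in the protocol itself, so this is not detail that would normally wait for a statistical analysis plan.

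**Working it through.** **Inputs from the protocol.** Ten sessions, five per week, one re-test at the end of therapy, 30 patients, threshold 0.05.

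**Inputs that are assumed.** Red-cell life L of 90-120 days, or an HbA1c half-life h of 25-35 days; SD of HbA1c change 0.2 to 1.0 points; 15 patients per group; two-sided test on changes.

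**Step 1: the protocol's own figure.** 10 sessions / 5 per week = 2 weeks, as stated. Counted from the first to the last session day, with both weeks starting on the first session day, it is 12 days. Hence t = 12 to 14.

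**Step 2: share of a sustained step change in glycaemia visible at day t.**
- Linearly declining weights (red-cell ages uniform on 0 to L, glycation proportional to exposure): 1 − (1 − t/L)².
- Plain average over L days: t/L.
- First-order turnover: 1 − 0.5^(t/h).

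| Model | Day 12 | Day 14 |
|---|---|---|
| Declining weights, L = 120 / 90 | 0.190 / 0.249 | 0.220 / 0.287 |
| Plain average, L = 120 / 90 | 0.100 / 0.133 | 0.117 / 0.156 |
| First-order, h = 35 / 25 | 0.212 / 0.283 | 0.242 / 0.322 |

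The overall range is 0.10-0.32. The result depends on the weighting model: at day 14, declining weights give 22-29% and a plain average 12-16%. Under every model at least two-thirds of a sustained effect is still to come.

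**Step 3: what an observed difference of 0 would leave open.** The 95% half-width is t(0.975, 28) × SD × √(2/15) = 2.048 × 0.365 × SD. Dividing by the share gives the largest sustained effect still compatible with the data.

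| SD of change | Half-width at two weeks | Compatible effect, share 0.287-0.220 | Compatible effect, share 0.322-0.100 |
|---|---|---|---|
| 0.2 | 0.150 | 0.52-0.68 | 0.47-1.50 |
| 0.3 | 0.224 | 0.78-1.02 | 0.70-2.24 |
| 0.5 | 0.374 | 1.30-1.70 | 1.16-3.74 |
| 1.0 | 0.748 | 2.61-3.40 | 2.3-7.5 |

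A 10/20 split is slightly worse: for SD 0.5, 1.38-1.81 in place of 1.30-1.70.

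**Step 4: power at two weeks** (noncentral t, two-sided 0.05, share 0.220-0.287). For a sustained 1.0-point effect: 83-97% at SD 0.2, 49-72% at 0.3, 21-33% at 0.5, 9-12% at 1.0.

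**Step 5: a check against overstatement.** Carry-over damps the variation in change as well as its mean, so the SD at two weeks should not be equated with the SD at full expression. Take a true response SD of 1.0, undamped error SD of 0.3 and a mean effect of 1.0. At two weeks the SD is √((share × 1.0)² + 0.3²) = 0.37 or 0.42, and power is 35-45%. At full expression the SD is √(1.0² + 0.3²) = 1.04, and power is 72%. The loss is real but smaller than a fixed SD would suggest.

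**Step 6: a shorter-window marker.** For glycated albumin or fructosamine with an assumed protein half-life of 20 or 17 days, 1 − 0.5^(14/h) = 0.384 or 0.435. Using first-order kinetics for HbA1c too, the ratio runs from 0.384/0.322 = 1.2 to 0.435/0.242 = 1.8.

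**The case against.** The strongest objection is that the yardstick is not the protocol's. The title speaks of short-duration therapy, the test comes at the end of that therapy, and nowhere is a sustained or fully expressed effect claimed. If any effect on glycaemia stops with the last session, no fuller HbA1c effect follows, and the end of therapy is close to the best time to look. This stands: a reader might infer that the protocol promises a lasting glycaemic effect and fails to measure it, and the text does not support that. What remains is that even two weeks of altered glycaemia enters HbA1c only in part.

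Second, every magnitude is imported. Power for a 1.0-point effect runs from 9% to 97% with the assumed SD, even under one kinetic model. At SD 1.0 the half-width is 0.75 points with full expression as well, so sample size alone makes a null weak evidence against moderate effects. This also stands, and it is why the size is given as a range.

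Third, the text is in the past tense and headed as an article, so sampling may be over. That limits the remedy rather than the point. Wording of a conclusion often belongs to a later document, but the outcome and its draw time are set here.

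Fourth, patients entered the hyperbaric group by their own willingness. That confounds the HbA1c contrast whenever blood is drawn, and none of the figures above account for it. It is a separate and larger matter.

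**Conclusion.** The point holds in limited form. HbA1c at the end of the two-week course is an attenuated outcome: about 10-32% of a sustained change would show, under the assumed kinetics. With 30 patients split 15/15, SD of change 0.5 and an observed difference of 0, sustained effects of up to about 1.2-3.7 points are not excluded. Only a very small SD, near 0.2, brings that limit down to about 0.5-0.7 points, and then only under the declining-weight or first-order models.

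A reader might go further and conclude that a two-week HbA1c is blind to treatment. It is not: a large effect, or a moderate one with a small SD, could be detected, and a null would count against a very large effect. Nor does the point reach leukocyte count or creatinine, since the argument rests on red-cell turnover.

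The change is worth considering rather than essential: one of three named outcomes is affected, the size rests on assumptions, and the protocol claims no sustained effect.

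**What to change.** 1. Analyse two-week HbA1c with baseline HbA1c as a covariate. This needs no new data.
2. State that two-week HbA1c is an early, partial reading: a null result is inconclusive about glycaemic effect, and a non-null one is not the full effect. This costs nothing.
3. If draws are still to come or blood was kept, which the protocol does not say, also assay glycated albumin or fructosamine at the two existing draws and name it the two-week glycaemic outcome. That is 30 patients × 2 draws = 60 assays. At an assumed 17-20 day half-life it is about 38-43% expressed at day 14, or 1.2-1.8 times the HbA1c share with first-order kinetics for both.

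The third step has drawbacks. The marker is less familiar and still partial, and because the baseline draw precedes debridement it carries more of the acute pre-debridement state. A gain in power is not shown, since its SD is unknown. If sampling is complete and no blood was kept, only the first two steps apply. None of the three removes the confounding from grouping by patient willingness.

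### HbA1c is sampled on either side of foot surgery and red-cell transfusion is not recorded, so if one occurs in between, the dilution it causes is read as better glycaemia

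*Protocol*

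**What the plan says.** All references are to the Methods section of the protocol.

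- **Aim** (first paragraph). A fall in HbA1c is an intended effect of treatment: "to decrease HbA1c levels, leukocyte count, and serum creatinine levels in DFU patient Wagner 3-4".
- **Pretest** (second paragraph). "All patients were taken blood test for HbA1c levels, leukocyte count, and serum creatinine levels before debridement".
- **Posttest** (second paragraph). "At the end of therapy, all blood tests were performed again in both groups".
- **Interval** (second paragraph). For the hyperbaric course: "This therapy is given five sessions in a week, so it takes two weeks". No separate duration is given for standard therapy.
- **Surgery** (third paragraph). Inclusion requires that patients "underwent debridement with or without toe amputation".
- **Exclusions** (third paragraph). "The exclusion criteria were patients who had severe organs dysfunction such as heart failure, pulmonary infection, pneumothorax, chronic obstructive pulmonary disease, and stroke". Transfusion, anaemia, haemoglobin and blood loss are not mentioned here or elsewhere.
- **Grouping** (first paragraph). Patients choose: "if they are willing to participate in the study but do not want to use HBOT was grouped to standard therapy".
- **Analysis** (fourth paragraph). "Analysis pretest and posttest values on both groups were used paired T-test and independent T-test". There is no rule for a reading that has become invalid.

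**The concern.** HbA1c is the glycated share of the haemoglobin in circulation. It serves as a measure of glycaemia only while the circulating red cells are the patient's own. Donor cells come mostly from people without diabetes, so a transfusion lowers the measured share at once while glucose stays the same.

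Because the two samples straddle an operation on a Wagner 3-4 foot, a transfusion between them is possible, and the protocol has no means of noticing it. Followed as written, it would score such a patient as improved.

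This is a different problem from the slow response of HbA1c to treatment. Slowness shrinks a real effect, whereas dilution between the samples produces an apparent effect in the hoped-for direction. With thirty patients in all, a handful of such readings could matter.

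**Working it through.** **1. Interval.** Ten sessions at five per week: 10 / 5 = 2 weeks. This reproduces the protocol's figure for the hyperbaric group. Since the pretest precedes debridement and the posttest follows treatment, the operation falls between the two samples.

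**2. Dilution per patient.** None of these inputs is in the documents, so all are assumptions: own red-cell volume V = 1.2 to 1.8 L, 180 mL of red cells per unit, two units (0.36 L), donor HbA1c 5.3%, patient HbA1c 8 to 12%.

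Donor fraction f = 0.36 / (V + 0.36). Fall = f × (patient HbA1c − 5.3).

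| V (L) | f | Patient HbA1c (%) | Fall (points) |
|---|---|---|---|
| 1.8 | 0.36/2.16 = 0.167 | 8 | 0.167 × 2.7 = 0.45 |
| 1.5 | 0.36/1.86 = 0.194 | 10 | 0.194 × 4.7 = 0.91 |
| 1.2 | 0.36/1.56 = 0.231 | 12 | 0.231 × 6.7 = 1.55 |

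A second model weights by haemoglobin. It assumes donor HbA1c 5.5%, a rise of 1 g/dL per unit and a haemoglobin of 7 to 10 g/dL before transfusion. For two units from 10% at 8 g/dL, the posttest is (8 × 10 + 2 × 5.5) / 10 = 9.1%, a fall of 0.9. Over the same 8 to 12% range the fall is 0.42 to 1.44. The two models agree closely.

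**3. Shift in a group mean.** Assume 15 per group; the protocol gives only the total of thirty. The transfusion rate is unknown, so it is varied from zero.

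- Nobody transfused: shift 0.
- Three of 15 transfused (3/15 = 0.2): 0.2 × 0.45 = 0.09; 0.2 × 0.91 = 0.18; 0.2 × 1.55 = 0.31 points.

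**4. Effect on the tests.** This was simulated with no true change, 15 per group, change scores, two-sided 5% tests, 40,000 replicates and an assumed SD of change of 0.5 or 1.0. Each patient in one group has a 20% chance of transfusion, and in the other 0%.

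| Fall per transfused patient | Mean shift | Paired test rejects (SD 1.0 / 0.5) | Between-group test rejects (SD 1.0 / 0.5) |
|---|---|---|---|
| 0.5 | 0.10 | 6.1% / 9.7% | 5.7% / 7.8% |
| 0.9 | 0.18 | 9.3% / 16.6% | 7.5% / 12.9% |
| 1.5 | 0.30 | 14.3% / 23.8% | 10.8% / 20.5% |

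When the chance is equal in both groups (20% or 40% in each), the between-group test rejects in 4.8% to 5.4%, close to nominal. The paired test stays inflated: at 40% and a fall of 0.9 it rejects in about 22% to 49%.

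**5. Direction.** Steps 2 to 4 concern a transfusion between the samples. One shortly before the pretest lowers the pretest value, so the later change is pushed towards apparent worsening.

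**The case against.** The strongest objection is that the triggering event is not in the document. The protocol does not say that anyone is transfused, the operation may be no more than debridement, and three of 15 is an illustration without a source. That stands: the bias is conditional, and its lower bound is zero.

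Two stronger readings are tempting, and the documents support neither. A reader might infer that the within-group HbA1c fall is biased towards improvement in both groups. That would need transfusions between the samples in both groups, and earlier transfusions act the other way. A reader might also infer that the group comparison is biased. It is biased only if transfusion differs by group. Grouping by patient choice, with nothing to balance the extent of surgery, means a difference cannot be ruled out; it does not show that there is one.

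It can also be said that setting readings aside is a matter for a statistical analysis plan, which is not at hand. This stands in part: that every posttest enters the analysis is an inference from silence, and a later plan could add a rule. It could not apply one to transfusions that were never captured, and what to record belongs in the protocol.

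Finally, dropping transfused patients conditions on an event after baseline that may track severity. That is a fair reason not to make the reduced set the only main analysis. It is also true that grouping by choice is the larger weakness of the comparison, and unequal transfusion would be one part of it.

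**Conclusion.** The point holds in conditional form. The samples straddle surgery, and the protocol can neither detect a red-cell transfusion nor distinguish dilution from a glycaemic change. Where a transfusion falls between the samples, the paired test counts it as improvement; the between-group test is affected only through a difference between groups.

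Per patient given two units, the fall is about 0.45 to 1.55 points. For a group mean it runs from 0 with nobody transfused to about 0.09 to 0.31 points with three of 15. These figures rest on the assumed red-cell volume, unit size, donor and patient HbA1c, and an even split of the thirty patients. The protocol states no expected HbA1c effect, so the shift cannot be expressed as a share of one. It is a worthwhile correction at moderate confidence, and it does not show that the HbA1c result is wrong.

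**What to change.** Add one chart item and a short protocol passage:

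1. Record any red-cell transfusion from three months before the pretest to the posttest, with its date, so that those before the pretest can be told from those between the samples.
2. Report the number of transfused patients per group.
3. Analyse HbA1c twice, with all patients and without transfused patients, and claim an HbA1c effect only if it holds in both. Leukocyte and creatinine values of transfused patients stay in their analyses.

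The cost is small: a look at the chart and slightly fewer patients in one of the two HbA1c analyses. Those removed may be the more severe cases, which is why the all-patient analysis stands beside the reduced one. If nobody was transfused, the two analyses coincide and the report can say so. The change concerns recording and analysis only and sets no rule on when to transfuse.

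### The only between-group test is an unadjusted t-test, so any difference in Wagner grade or toe amputation between self-selected groups is counted for or against HBOT

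*Protocol*

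**What the plan says.** All of this stands in the Methods section of the protocol.

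- **Eligibility.** Type 2 diabetes with "DFU Wagner class 3 or 4, aged over 18 years, and underwent debridement with or without toe amputation". Every patient is debrided; toe amputation is an addition in some.
- **Allocation.** Patients who accept HBOT form the combination group; "if they are willing to participate in the study but do not want to use HBOT was grouped to standard therapy". Nothing randomises, stratifies or matches.
- **Timing.** Blood is drawn for "HbA1c levels, leukocyte count, and serum creatinine levels before debridement, then grouped for standard therapy or standard therapy with 10 sessions of HBOT". The second sample comes later: "At the end of therapy, all blood tests were performed again in both groups".
- **Size.** "Thirty diabetic patients with DFU Wagner 3-4 were participated in this study". The split between groups is not given.
- **Analysis.** "Analysis pretest and posttest values on both groups were used paired T-test and independent T-test", judged at 0.05. No covariate or stratum is named, and the text does not say whether the independent test compares posttest values or changes.

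**The concern.** Three features combine.

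1. Patients choose their group, so grade and operation may differ between groups systematically as well as by chance.
2. The pretest sample precedes surgery and the posttest follows it. Any effect of the operation therefore lies inside the measured change. Neither a change score nor adjustment for the pretest value removes it, because two patients with the same leukocyte count before surgery may be expected to differ afterwards if only one lost an infected toe.
3. The one between-group test named takes no covariate.

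A difference in grade or operation between groups would then be read as an effect of HBOT, in either direction: it could create an apparent benefit or hide a real one. The mechanism is a clinical inference that the protocol does not state. It is most plausible for leukocytes, and less so for creatinine or for HbA1c over two weeks. Because the protocol itself fixes the test, this is a stated choice and not a detail left to a later plan.

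**Working it through.** **Plan's own figure.** There is none to reproduce: the protocol gives no power, effect size, SD or sample-size derivation.

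**From the protocol.** N = 30; unadjusted independent t-test; level 0.05.

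**Assumed, not in the protocol.** 15 per group; two-sided test; residual SD 1; no HBOT effect; toe amputation lowers the marker by g SD, with g = 0.5 or 1; amputation shares p1 (HBOT group) and p0 (standard group). For the two-factor model, Wagner grade has the same shares as amputation, is independent of it within group, and has no effect on the marker. The pretest value is left out of the simulation.

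**Bias of the t-test.** Bias = −g × (p1 − p0).
- g = 1, 60% v 30%: −1 × 0.30 = −0.30 SD.
- g = 0.5, 60% v 30%: −0.5 × 0.30 = −0.15 SD.
- g = 1, 60% v 40%: −1 × 0.20 = −0.20 SD.

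**Rejection when HBOT does nothing** (simulated, 20,000 to 40,000 trials per setting; small differences between runs are simulation error).

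| Shift g | Amputation shares | t-test | Adjusted for amputation |
|---|---|---|---|
| 1 SD | 60% v 30% | about 11% | 5% |
| 1 SD | 60% v 40% | about 8% | 5% |
| 0.5 SD | 60% v 30% | about 6.5% | 5% |
| 1 SD | 40% v 40% | 5% | 5% |

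The return to 5% holds because amputation is the only confounder in the simulation.

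**Price of adjustment: mean 95% half-width in SD, t-test against the model with amputation and grade.**

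| Setting | t-test | Two-factor model | Change |
|---|---|---|---|
| Neither factor matters, both 40% v 40% | 0.742 | 0.774 | 0.774/0.742 = 1.04, 4% wider |
| Neither factor matters, both 60% v 30% | 0.741 | 0.859 | 0.859/0.741 = 1.16, 16% wider |
| g = 0.5, both 40% v 40% | 0.763 | 0.772 | 0.772/0.763 = 1.01, 1% wider |
| g = 0.5, both 60% v 30% | 0.762 | 0.858 | 0.858/0.762 = 1.13, 13% wider |
| g = 1, both 40% v 40% | 0.826 | 0.772 | 0.772/0.826 = 0.93, 7% narrower |

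The interval narrows only in the last row, where the factor is strong and balanced.

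**Degrees of freedom.** Intercept, group, pretest, grade and amputation are 5 parameters, so 30 − 5 = 25 residual degrees of freedom remain.

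**The case against.** - **The magnitudes are assumed.** This stands. Group split, shares and shift are all absent from the protocol. Since every patient is debrided, only the effect of amputation beyond debridement matters, and its size is unknown. Patients who need amputation may also be sicker, so even the sign is uncertain.
- **The operation may not be a baseline variable.** This stands, and it limits the fix. Surgery follows the pretest sample, and the text does not say whether the operation was settled before or after grouping. If after, conditioning on it could itself add bias.
- **The root defect is allocation by preference.** This also stands. A reader might infer that the adjusted model would be free of bias; that is true only in a simulation with one confounder. Adjustment leaves all other self-selection in place.
- **Chance imbalance proves the point.** A reader might infer this from the fact that, with 40% in both groups, a gap of at least 3 patients has probability 0.35. It does not: with equal underlying shares the t-test still rejects about 5% of the time. The bias argument needs shares that differ systematically, which preference allocation permits but the protocol does not show.
- **Mixing grades and operations is the study's intended population.** Agreed. Admitting both is not an error. The weakness lies in combining that eligibility and preference allocation with a test that ignores both factors.
- **Covariates are commonly left to a statistical analysis plan.** That would answer the point if the protocol were silent, but it names the test.

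**Conclusion.** The point holds in limited form. The protocol fixes an unadjusted between-group test in a self-selected comparison whose pretest precedes surgery, so a difference in grade or operation would pass into the HBOT estimate. Under the assumed values the bias is 0.30 SD with about 11% false rejection (1 SD shift, 60% v 30%), falling to 0.15 SD and about 6.5% at a 0.5 SD shift; it is zero if the shares are equal.

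Two stronger readings are not supported. One is that surgery does masquerade as an HBOT benefit in this study: the protocol reports no imbalance and no effect of operation on any marker, and the distortion could run either way. The other is that adjustment will sharpen the estimate: at a 0.5 SD shift the gain in precision is already gone. The case for adjusting is less bias. A change to the analysis is worth making, but it does not repair the allocation.

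**What to change.** 1. Tabulate Wagner grade and operation by group, and state whether the operation was settled before or after grouping.
2. For each marker, make the between-group analysis a linear model of the posttest value on group, pretest value, Wagner grade (3 or 4) and toe amputation (yes or no). Keep the independent t-test as the unadjusted result.
3. Include toe amputation in the main model only if the operation was settled before grouping. Otherwise leave it out of the main model and report the version that includes it as a sensitivity analysis.
4. State that adjustment for these factors does not remove other bias from self-selection.

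**Cost.** A few sentences and one table. Eligibility already defines both factors, so no new data should be needed. The statistical price is two more parameters than a model with group and pretest alone and, if neither factor matters, an interval about 4% wider than the t-test's when both are balanced and about 16% wider when both are 60% v 30%.

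### The only between-group test is an unadjusted independent t-test, although patients choose their own arm and every patient has a pretest value

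*Protocol*

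**What the plan says.** All of this is in the Methods of the Protocol.

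- **Design and aim.** "This study uses pretest and posttest control group design"; the aim is "to decrease HbA1c levels, leukocyte count, and serum creatinine levels in DFU patient Wagner 3-4".
- **Allocation.** The patient decides. "If they are willing to participate in the study and use HBOT was grouped to combination therapy", and "if they are willing to participate in the study but do not want to use HBOT was grouped to standard therapy".
- **Measurement.** "All patients were taken blood test for HbA1c levels, leukocyte count, and serum creatinine levels before debridement"; later, "At the end of therapy, all blood tests were performed again in both groups". Each endpoint therefore has a before and an after value in both arms.
- **Size.** "Thirty diabetic patients with DFU Wagner 3-4 were participated in this study". The split between arms is not given.
- **Analysis.** "Analysis pretest and posttest values on both groups were used paired T-test and independent T-test", with significance at p < 0.05. No regression model, covariate, matching or stratification is named.

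**The concern.** A paired t-test asks whether values moved within one arm. It says nothing about HBOT against standard therapy, so that question rests wholly on the independent t-test. The sentence applies the tests to pretest and posttest values and does not mention changes. The nearest literal reading is an independent t-test on the posttest values, perhaps with another on the pretest values.

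Under randomisation such a posttest test would be inefficient but unbiased. Here people who accept HBOT may differ from those who decline it in the very laboratory values under study. A posttest-only comparison counts whatever part of that difference persists as a treatment effect. If acceptors start better, an effect can appear where there is none; if they start worse, a real benefit can be hidden. This applies to all three endpoints in the title. A separate t-test on the pretest values corrects nothing, and with 30 patients it will miss most moderate gaps.

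**Working it through.** The Protocol states no power, SD or effect size, so there is no figure of its own to reproduce. The calculation shows how large the problem could be.

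**Inputs from the Protocol:** N = 30; alpha 0.05; self-selected arms; pretest and posttest values in all patients.

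**Assumptions:** 15 per arm; two-sided test; within-arm SD 1 at both times; pre-post correlation r from 0.3 to 0.9; expected baseline gap D of 0.3, 0.5 or 0.8 SD; no HBOT effect unless stated.

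**Selection mechanisms considered**

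- *Through the baseline:* the arms differ only through the measured pretest. The expected posttest gap is rD.
- *Stable difference:* the arms differ by D at both times and the pretest measures this with noise. The expected posttest gap is D.
- *Unmeasured:* the arms have equal baselines and differ by D at posttest for other reasons.

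**Bias of each analysis**

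| Analysis | Through baseline | Stable | Unmeasured |
|---|---|---|---|
| Posttest t-test | rD | D | D |
| Change t-test | (r − 1)D | 0 | D |
| Linear model on group and pretest | 0 | (1 − r)D | D |

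**Posttest t-test, D = 0.5, r = 0.7.** The standard error is √(2/15) = 0.365 SD, with 28 degrees of freedom.

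- Through the baseline: bias 0.7 × 0.5 = 0.35; noncentrality 0.35/0.365 = 0.96; false-positive rate 0.153.
- Stable: bias 0.50; noncentrality 0.50/0.365 = 1.37; false-positive rate 0.262.

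**Change t-test, same case.** The SD of a change is √(2(1 − 0.7)) = 0.775.

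- Through the baseline: bias −0.3 × 0.5 = −0.15; noncentrality −0.15/(0.775 × 0.365) = −0.53; rate 0.081.
- Stable: no bias; rate 0.05.

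**False-positive rates by simulation (60,000 trials per cell), D = 0.5, r = 0.7**

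| Mechanism | Posttest | Change | Linear model |
|---|---|---|---|
| Through baseline | 0.153 | 0.079 | 0.049 |
| Stable | 0.264 | 0.052 | 0.083 |
| Unmeasured | 0.263 | 0.397 | 0.443 |

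The simulated rates agree with the noncentral t results where both exist.

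**Range for the posttest t-test over r = 0.3 to 0.9 and the first two mechanisms:** about 6% to 12% at D = 0.3, 7% to 26% at D = 0.5, and 10% to 56% at D = 0.8. With arms of 20 and 10, D = 0.5 and r = 0.7 give 14% and 24%.

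**A pretest t-test as a balance check.** Its power is 0.125 at D = 0.3, 0.262 at D = 0.5 and 0.562 at D = 0.8. Among simulated trials where it is non-significant (D = 0.5, r = 0.7), the posttest comparison is still biased by 0.24 SD (through baseline) or 0.39 SD (stable).

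**Masking.** Let the true benefit be 0.8 SD and let acceptors start 0.5 SD worse, with r = 0.7. The apparent posttest benefit falls to 0.80 − 0.35 = 0.45 SD or 0.80 − 0.50 = 0.30 SD. The posttest t-test then detects it in 22% or 12% of trials, against 56% with no gap. The linear model detects it in 80% or 63%, and the change comparison in 90% or 78%. The 90% is flattered by that analysis's own bias of −0.15 SD.

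**The case against.** **The independent t-test may have been meant for changes.** The sentence does not say which variable is tested, and a pretest-posttest design that aims at a decrease lends this reading some support. The pretest would then be in the comparison, and false positives in the main case would be 5% to 8%, not 15% to 26%. This stands as a limit on size: the larger figures belong to the posttest reading. It does not clear the plan. The text names values, not changes. A change comparison without adjustment also fails where correlation is low: at D = 0.5 and r = 0.3 with selection through the baseline, it gives 12% false positives, worse than the posttest test's 7%.

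**Covariates are commonly left to a SAP, which may exist.** That would answer a complaint about missing detail. Here the Protocol names its test and its significance rule, and the named test does not suit the stated allocation.

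**The root problem is the allocation, and adjustment leaves it in place.** This is true. With an unmeasured difference of 0.5 SD, all three analyses keep the full bias, and the more precise ones flag it more often (44% for the linear model against 26% for the posttest test). Nothing in the Protocol shows which mechanism operates. Adjustment removes only what the pretest carries, but leaving out the one confounder measured in every patient is avoidable.

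**Two analyses on three endpoints give six results.** This is fair, and it is why one analysis should be designated as the main one in advance.

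**The text is in the past tense.** If the data are in hand, the change is a re-analysis and must be labelled so.

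**Conclusion.** The concern holds. The only between-group method named is unadjusted, the arms are formed by patient preference, and the pretest that could reduce the resulting bias is available for everyone.

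How far results would be distorted cannot be known from the Protocol, because the arm sizes, baseline gap, correlation and selection mechanism are all assumed here. A moderate gap is enough to raise the false-positive rate of a posttest comparison to several times its nominal level, or to hide a large benefit. Both analyses that use the pretest do better in the main case when selection runs through the baseline or reflects a stable difference, but neither is best under both. No analysis of these three values supports a causal claim on its own. This should be fixed; it does not by itself make the data unusable.

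**What to change.** Replace the independent t-test as the basis for comparing arms. For each endpoint:

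1. As the main analysis, fit a linear model of the posttest value on group and pretest value. Report the adjusted HBOT-minus-standard difference with its 95% confidence interval.
2. Report the between-group comparison of changes beside it as a sensitivity analysis. If the two disagree, say so and treat the finding as dependent on how patients selected themselves.
3. Do not take a non-significant t-test on pretest values as evidence that the arms are comparable.
4. Describe the result as a non-randomised association.

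**Cost.** Two or three sentences in the analysis paragraph, and no new measurement. The model spends one degree of freedom: if r = 0 the variance rises by a factor of 1 + 1/26 = 1.04. Precision can also suffer if correlation is low and imbalance large. With no expected gap and 15 per arm, the approximate 95% half-width is 0.75 SD for the posttest t-test; for the model it is 0.76 SD at r = 0, 0.66 SD at r = 0.5 and 0.55 SD at r = 0.7. If the data have already been seen, label the analysis post hoc.
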